### **Power:**

Our study is powered from a pilot study of ankle alignment during static phases of gait. Refer to Figure 3-6, Left: OA participants (group 1, 30 participants with 3 trials per subject, n=90) vs. Plot 1, Right: controls (group 2, 20 participants with 3 trials per subject, n=60).

Power analysis for coronal plane misalignment: Assumptions: mean = -1.8 degrees SD=1.8 degrees n=90 (30x3) for an OA group, and mean=1.7 degrees, SD=2.9 degrees, n=20 for the controls (valgus or varus) with 3 trials per subject and within subject error of 1.5 degrees. Based on 5000 simulated datasets and performing the mixed regression model described in H1, there is >99% power to detect the difference between groups, i.e., 3.5 degrees, as statistically significant, at p=0.05.

Coronal alignment is the measure that yields ankle varus, neutral or valgus. This demonstrates an appropriate sample size for the effect size of ankle alignment. Additionally, the pilot study did not differentiate between varus or valgus alignment. Due to demographics, it is possible that all six participants were varus or neutral. We suspect that cleaner separation of groups for comparison will only improve our ability to detect significant differences between groups.

### **5.7 Withdrawal of Participants**

This is not a treatment study; withdrawing or being terminated from this study will not have an impact on participant safety. A study clinician or the PI may withdraw a participant without their consent if he or she feels that it is not in a participant's best interest to continue in the study or if they are unable to complete the study procedures. All data previously collected from participants who withdraw, or are withdrawn, will be kept and may be used in the study data analysis.

Participants may withdraw at any time by informing the Research Coordinator and/or the PI.

### **6.0 Reporting**

All safety information on Adverse Events (AEs), Serious Adverse Events (SAEs), unanticipated events or problems, and protocol deviations will be collected. This information will be collected at study visits and whenever participants call to report a problem. It will be collected on VA IRB forms (Report of a SAE and/or Problem Form), or Report of Problems (ROP) Form. Safety data will be collected on an as-needed basis and will begin upon enrollment into the study. Any anticipated AEs will be recorded

on a log sheet and reported annually with the CRQ. Although the risks identified in this study are relatively minimal, we will tabulate a list of any such reports that occur during the study and compare it with corresponding data available in the literature. This will allow us to analyze how much of an increased risk was due to the administered protocol. Also please note, the anticipated maximum radiation dosage (0.47 mSv) is far below any dose that would have a measurable effect on participants. After each report of an AE, SAE or an unanticipated problem, we will evaluate study procedures for previously-assessed risks, and will determine whether any changes to the protocol are necessary to minimize risks. The study will be suspended until these changes have been fully implemented and approved by the IRB.

If we become aware of relevant findings or information that may affect participants' health or welfare we will contact participants by phone and/or a letter to notify them.

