## **5.5 Study Visits, Data Collection, and Risk Management**

All data collection procedures will be performed at the VA Puget Sound. There are several components to the study. Participants may be asked to complete some or all components of the study depending on their eligibility, but may do so over several visits (up to 4). We anticipate that most participants will complete all study components within 3 visits over a 3-4 month timeframe, but participant schedules and the accessibility of facility resources (i.e., the ability to schedule time slots with the Dept. of Diagnostic Imaging) may extend the study timeframe beyond this estimate. We will attempt to conduct multiple components of the study during each visit in order to minimize the number of visits required for participation. Visits may last up to 5 hours each. Study visits will be scheduled by contacting the participants on phone, or during in-person contacts. We may contact participants with appointment reminders via email or phone.

During study sessions, visitors and observers will not be allowed in the lab unless the participant agrees to their presence; the participant can change her/his mind at any time.

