### **Standing Long Leg X-ray**

If needed, this component will be performed at the VAPSHCS Department of Diagnostic Imaging. Participants will stand still while a frontal X-ray of the hips down is taken. This will allow us to quantify

the alignment at the hip, knee and ankle. We will also take standard foot alignment X-rays, including anterior/posterior and medial/lateral views of the feet.

We will measure the ankle alignment, if a participant is determined to have an ankle alignment type for which the study group is already full, that individual will not be able to participate further in the study, but will be compensated for the visit.

Please note, for participants that do not have a clinical diagnosis of alignment type (those with and without OA), we do not intend to inform them if we note misalignment. It is unknown at this time if ankle misalignment is causative to the development of ankle OA or if it is clinically relevant to prevention or conservative treatment of OA; these are some of the questions that this study hopes to address. Therefore, the information would not be useful to participants.

The CT scan and Biplane Fluoroscope session will be conducted in no particular order and may be conducted over multiple visits.

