#### Wedge insole comfort

It is possible, although unlikely due to the brief nature of the data collection trials, that participants may experience discomfort or pain while standing and walking with the wedged insoles or study shoes. If this occurs it would likely be discovered immediately at the start of testing for a given wedge condition. Participants may experience mild soreness or soft tissue irritation (e.g., a blister) from walking with shoe inserts and/or in shoes that are unfamiliar, either during or shortly after the study sessions. Participants with ankle OA may experience a small increase in ankle or foot pain during or shortly after the study sessions. Participants will be instructed to inform us if they feel discomfort or pain and the procedures will be stopped so that we can adjust/re-fit the shoe/insole. If we are unable to achieve a comfortable fit the study session will be ended. Care will be taken to properly fit the shoes. Participants can take breaks at any time.

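### Mild soreness or pain that starts after a participant's last walking session is recorded only if the participant calls, which weakens the planned safety comparison with the literature

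*Combined protocol and SAP*

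**What the plan says.** Section 6.0 (Reporting) undertakes to collect all adverse events and describes how: "This information will be collected at study visits and whenever participants call to report a problem". It adds: "Safety data will be collected on an as-needed basis and will begin upon enrollment into the study". A start is given but no end. The reports are to be tabulated and set against published data, to judge how much added risk the study procedures caused.

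Section 5.5 (Wedge insole comfort) names the likely minor harms and their timing. Soreness or soft-tissue irritation from unfamiliar shoes or inserts may appear "either during or shortly after the study sessions". For the OA groups: "Participants with ankle OA may experience a small increase in ankle or foot pain during or shortly after the study sessions". The same paragraph has a reporting instruction: "Participants will be instructed to inform us if they feel discomfort or pain and the procedures will be stopped". The action that follows is to re-fit the shoe or insole or, failing that, to end the session.

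On visits, section 5.5 allows up to four and says: "We anticipate that most participants will complete all study components within 3 visits over a 3-4 month timeframe". On sequence, the Standing Long Leg X-ray subsection says: "The CT scan and Biplane Fluoroscope session will be conducted in no particular order and may be conducted over multiple visits".

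**The concern.** The plan names a class of event that can begin after the participant has gone home, yet schedules no contact to ask about it. If another visit follows, staff can pick the event up then, although no standard question is specified. If the walking session was the last visit, the event reaches the log only when the participant decides to call. People seldom have a strong reason to report a blister or a day of extra ankle pain to a study they have finished.

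At stake is the reading of the event list. Section 6.0 gives it an analytic purpose, the comparison with the literature. A count with unknown ascertainment and no stated denominator cannot be compared fairly with a published rate, and the error would tend to make the procedures look better tolerated than they are.

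**Working it through.** The plan states no event rate or reporting rate, so there is no figure of its own to reproduce. The check has two parts.

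**1. The passages side by side**

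- *Can events be delayed?* Yes. Wedge insole comfort places soreness, irritation and increased pain either within a session or soon after it.
- *Which routes capture them?* Section 6.0 names study visits and participant calls. The staff-initiated contacts described after enrollment are for scheduling and appointment reminders (section 5.5) and for passing on findings relevant to health (section 6.0). None asks about events.
- *Does the reporting instruction fill the gap?* Not as written. Its consequence, stopping to re-fit, applies only while the session is running.
- *Can a walking session be the last visit?* Yes. The order of CT and fluoroscopy is open. Medical Record Review also lets existing CT scans and X-rays replace new ones, which can remove the other imaging visits. The documents do not say how often this will happen.

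So after a final walking session, self-report is the only remaining route.

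**2. How much could be missed**

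Let N be the number of participants whose last visit is a walking session, r the true proportion with an event starting after it, and c the proportion of those affected who call.

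- Events occurring = N × r
- Events recorded = N × r × c
- Missed share = 1 − c, whatever N and r are

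For illustration, N = 120, the maximum OA enrollment (section 5.1). This assumes that every OA participant ends on a walking session, so it is an upper bound. Both r and c are assumptions.

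| r | Events (120 × r) | Recorded, c = 10% | Recorded, c = 50% | Recorded, c = 90% |
|---|---|---|---|---|
| 5% | 6 | 0.6 | 3 | 5.4 |
| 10% | 12 | 1.2 | 6 | 10.8 |
| 20% | 24 | 2.4 | 12 | 21.6 |
| 30% | 36 | 3.6 | 18 | 32.4 |

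The missed share is 90%, 50% and 10% across the three columns. A true rate of 10% would appear as 10% × c, that is 1%, 5% or 9%. More than half of these events are missed only if c is below 50%.

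These figures concern only events that begin after the last session. Events during a session are collected at that visit, so the shortfall in the whole event list is smaller than 1 − c whenever some events start in session.

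**The case against.** The strongest reply is that the gap is narrow and the harms are slight. The protocol regards discomfort in the insoles or shoes as unlikely because the trials are brief, and thinks it would usually show at the start of a wedge condition. After-effects are described as possible and mild or small. Each walking session is itself a visit at which safety data are collected, and calls are an explicit second route. The consent form, not seen here, may tell participants to call. The study describes itself as not a treatment study, and no hypothesis test uses adverse events.

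Most of this stands, and it rules out several stronger readings that a reader might infer:

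- *That the plan expects these harms.* It says only that they may occur.
- *That delayed events are largely missed.* This needs a call-in share below one half, and the documents give none.
- *That nobody asks about harms.* In-session events are covered, and an earlier walking session is followed by another visit.
- *That capture differs between OA and control groups.* No section ties visit order to group, and no between-group safety comparison is planned.
- *That the harms of wedges are understated.* Participants walk in lab shoes without wedges and with them, and the protocol attributes soreness to inserts, shoes or both. Delayed symptoms cannot be assigned to the wedge.

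The reply does not close the gap itself. The protocol names delayed events, undertakes to collect all adverse events and plans to interpret the resulting list, but after a final walking session it has no active means of finding them.

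**Conclusion.** The point holds as a minor gap in safety reporting. Mild events that begin after a participant's last walking session are recorded only on the participant's initiative, so some under-recording is likely. Its size cannot be stated from the documents: it equals one minus an unknown call-in share, and the number of participants affected depends on an unknown share whose last visit is a walking session.

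The conclusion rests on the written collection routes being complete, and on some affected participants not calling. The consequence is confined to section 6.0, where the comparison with the literature would be biased toward a low event rate by an unknown amount. Hypotheses 1 to 4 and the power statement are unaffected. The change is worth making because it is cheap, not because the present plan is unsafe.

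**What to change.** In section 6.0:

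1. Add one short scripted contact by existing staff, by phone or email, a few days after each participant's last walking session. Ask about pain, soreness, skin problems and falls.
2. Where another visit follows a walking session, ask the same questions there.
3. State when event collection ends for each participant.
4. Tabulate events with the number of participants asked as the denominator. Describe them as effects of the session as a whole (shoes, insoles and walking), not of the wedges alone.

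The cost is at most 150 short contacts (up to 120 OA participants plus up to 30 controls), by staff who already contact participants about appointments, and a small protocol amendment. Asking will also bring in more mild events. Section 6.0 requires procedures to be evaluated after each adverse event report, so each one adds some work beyond the contact itself. The imaging, the visit schedule and the analyses of Hypotheses 1 to 4 do not change.

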### Research Design & Methodology:

Up to 120 participants with ankle OA (up to 40 with varus misalignment, up to 40 with valgus misalignment, up to 40 with neutral alignment) and up to 30 participants without ankle OA will be enrolled. Participants will be men and women, age 18-80 years, who are able to stand and walk for at least one hour without significant difficulty. Participants will undergo a series of radiological measurements including: a standard x-ray from the hips down, a set of x-rays of the legs, a CT scan from the knees down, up to 80 fluoroscopic images while walking or

standing. Participants will do the fluoroscopic trials with and without wedged shoe insoles. The radiological measurements will be used to address the aims outlined above.

At the end of this study we hope to: (1) have a better understanding of ankle arthritis, (2) be able to demonstrate the potential for an improvement upon the current clinical examination for ankle misalignment and/or OA, and (3) provide evidence for, or against, the use of shoe inserts to manage and/or treat ankle misalignment and/or OA. It is hoped that this work will aid future clinicians and researchers in delaying or preventing the onset of ankle OA in at-risk veteran and non-veteran patients.

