### **Eligibility Screening and Group Determination**

Participants will have been preliminarily screened during recruitment, then during the first visit, after informed consent is obtained, we will make a final eligibility determination. This will include verifying that the information collected during recruitment is accurate and current.

At each visit that involves exposure to radiation female participants of child-bearing potential (under age 50) will undergo a pregnancy test (urine test) so we can verify that they are not pregnant. Designated study staff will escort female participants to the bathroom and provide them with a specimen cup, pregnancy test strip, and a disposable container on which to place the used test strip. Staff will go over the test instructions, and verify the test result. Staff will not handle urine specimens, we will tell participants how to handle and dispose of the materials. If the test indicates that the participant is pregnant she will be not be able to participate in the study and we will advise her to see her regular clinical care provider. If a participant cannot continue in the study they will still be compensated for the visit.

Participants with ankle OA will be grouped based on their clinical diagnosis of ankle coronal plane alignment (varus, neutral or valgus) as noted in their medical record, and/or determined by reviewing/measuring ankle alignment in x-rays in the medical record during recruitment and screening. Participants with ankle OA who do not have a formal clinical diagnosis of alignment type, if

alignment type cannot be determined via the x-rays on file, or if there are no x-rays on file, will be categorized after undergoing the Standing Long Leg X-ray.

Participant weight and height will be measured, and his/her age, sex, race/ethnicity and Veteran status will be recorded. Participants will be asked to walk in a straight line in the hallway while a researcher times the subject to determine his/her natural walking speed.

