#### Biplane Fluoroscopy – Wedged Insoles

Research staff will insert one of the wedged insole configurations (selected based on the participants' varus/valgus indication) into both of the participants' shoes. Participants in the control group may be asked to do these procedures with several different insole configurations. Participants will then repeat the standing trial, and then perform walking trials in the same format described above. With some participants, we may capture images of each foot during the standing and walking X-ray procedures. Participants will be instructed to let us know if they feel pain or discomfort during the procedures. If the shoes or inserts feel uncomfortable, we will attempt to re-fit them, if we are unable to achieve a comfortable fit, we will stop the procedures.

We will not ask participants to walk through our active fluoroscopic imaging system more than 80 times total during the entire study, and as noted above the total radiation exposure for the study will not exceed 0.47 mSv.

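### Section 6.0 says that comparing reported events with the literature will show how much added risk the protocol caused; the design supports a description of events, not that attribution

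*Combined protocol and SAP*

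**What the plan says.** The only safety analysis in the document is in section 6.0, Reporting; section 5.6, Data Analysis, has none. Section 6.0 describes the method as follows: "we will tabulate a list of any such reports that occur during the study and compare it with corresponding data available in the literature". It then states what the method will yield: "This will allow us to analyze how much of an increased risk was due to the administered protocol".

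On how events are gathered, the same section says "This information will be collected at study visits and whenever participants call to report a problem" and "Safety data will be collected on an as-needed basis and will begin upon enrollment into the study".

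On who is exposed, the abstract's design paragraph says "Participants will do the fluoroscopic trials with and without wedged shoe insoles". Section 5.5 (Biplane Fluoroscopy – Wedged Insoles) adds "Participants in the control group may be asked to do these procedures with several different insole configurations".

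On the event most likely to be seen, section 5.5 (Wedge insole comfort) says "Participants with ankle OA may experience a small increase in ankle or foot pain during or shortly after the study sessions". On baseline data, section 5.5 (Eligibility Screening and Group Determination) says "Participant weight and height will be measured, and his/her age, sex, race/ethnicity and Veteran status will be recorded". It also provides for a timed walk, and the Medical Record Review adds diagnosis and treatment history. None of these is a pain or symptom score.

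**The concern.** The sentence promises a causal quantity: the part of the observed risk that the protocol produced. That needs an estimate of what would have happened to the same people without the study procedures. Such an estimate can come from an unexposed group, from the participants' own state beforehand, or from an external source matched on population, time window and way of asking. The plan provides none of these.

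At stake is one safety statement. Followed literally, section 6.0 would lead the study to report an excess risk, or the absence of one, that its data cannot establish.

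**Working it through.** The safety plan states no event rate, sample size, margin or test, so there is no figure of the plan's own to reproduce. The check is a reading of the design, followed by an illustration with assumed rates.

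**Possible sources of the comparison**

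1. *An unexposed group.* Section 5.1 plans up to 120 people with ankle OA and up to 30 controls. The controls differ from the others in OA status, not in exposure: they undergo the imaging and walking procedures and may be given several insole configurations. No group is kept off all procedures.
2. *The participant's own baseline.* The expected event in OA participants is an increase in pain. The abstract describes OA as already associated with moderate to severe pain. An increase needs a starting value, and the baseline items listed in section 5.5 contain none. The one baseline fact about symptoms is in section 5.4: controls with ankle pain are excluded.
3. *The literature.* Section 6.0 names no source, event definition, rate, denominator or time window. Section 5.5 expects about 3 visits over 3 to 4 months, possibly longer, so the window matters for any rate taken from elsewhere.

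**How much the missing background rate matters**

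Apparent excess = observed proportion − background proportion.

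The denominator, 120 OA participants, is the planned maximum. The event counts and the background rates are assumptions, since the documents give neither. Intervals are exact (Clopper-Pearson) 95% limits for the observed proportion.

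| Assumed reports of more pain | Observed (95% CI) | Background 5% | 10% | 20% | 30% |
|---|---|---|---|---|---|
| 12 of 120 | 10% (5.3 to 16.8) | +5 | 0 | −10 | −20 |
| 24 of 120 | 20% (13.3 to 28.3) | +15 | +10 | 0 | −10 |

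The last four columns are percentage points; for example, 12/120 − 0.05 = 0.10 − 0.05 = +5 points, and 12/120 − 0.20 = −10 points. Within each row the data are fixed and only the assumed background changes, yet the result runs from an excess to a deficit. Nothing in the documents selects a column.

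**The case against.** The strongest reply is that this is one loose sentence in a reporting section, placed among ethics-board forms and annual reports and introduced by a remark that the risks are small. No attributable-risk endpoint, estimator or test is defined, and no hypothesis uses the result. That stands, and it sets the severity. It does not make the sentence right: it is current text and it states what the comparison will deliver.

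Other replies stand in part:

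- *Some events need no baseline score.* A fall or a blister is recognisable without one. Insole discomfort is expected to show at once when a wedge condition starts, which gives some basis in time for attribution. New ankle pain in controls would also be recognisable. So the baseline argument applies to pain in OA participants and not to every event.
- *Trials with and without wedges give a within-person contrast.* They could for immediate insole discomfort. But both conditions belong to the protocol, no such safety comparison is planned, and pain arising after a session cannot be assigned to one condition.
- *External controls can be legitimate.* They can, with matched population, window and ascertainment. None of these is specified.
- *Symptoms or relatedness may be recorded elsewhere.* The screening scripts and reporting forms are not in the file, so this cannot be checked.

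A reader might also infer that the comparison would be biased toward reassurance because reports are passive. The documents do not support this. Events are also collected at visits, participants are told to speak up about pain or discomfort, and the literature is unnamed, so how its events were sought is unknown. Nor do the documents say that any such safety conclusion would be reported with the wedge-insole findings.

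**Conclusion.** The concern holds in a limited form. Section 6.0 claims an attribution that the design cannot deliver, because there is no group off all procedures, no specified external comparator and, for pain in OA participants, no baseline symptom score. The size and sign of any stated increase would depend on a background rate that the documents do not give: +5 to −10 percentage points in the example of 12 in 120 with assumed backgrounds of 5% to 20%. These figures illustrate the dependence and do not predict a result. The direction of error cannot be stated.

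The small numbers might tempt a reader to cite the limits for zero events (exact two-sided 95% upper limits of 2.4% for 150 participants and 8.8% for 40). Those describe precision, which is a separate matter from attribution.

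Severity is minor. The safety summary is secondary and Hypotheses 1 to 4 are unaffected.

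**What to change.** In section 6.0, delete the sentence that claims attribution and replace the literature comparison with a descriptive summary. Suggested text: *For each anticipated event (increase in ankle or foot pain, skin irritation, fall) we will report the number and proportion of participants affected, with exact 95% confidence intervals, separately for each OA alignment group and for controls. Published rates will be cited as context only and will not be used to estimate risk caused by the protocol.*

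The cost is a change of wording. The plan gives up a stated attributable-risk result, but one it could not validly produce.

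Optionally, a brief ankle or foot pain rating before and after each session and insole condition would make pain change measurable. It is a new data element, and it must fit sessions that may span several visits and include barefoot, neutral-insert and several wedge conditions. It would miss pain that begins after the participant leaves, and order and fatigue would affect differences between conditions. If it is added, describe the result as change during the session, not as risk caused by the protocol.
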